Analysis for Aim 4: For all subjects completing gadolinium enhanced cMRI myocardial perfusion imaging, ¹³N-Ammonia PET perfusion imaging, ¹¹C-Acetate PET imaging and cMRI fibrosis imaging, the relationships between myocardial blood flow reserve, oxidative metabolism, and fibrosis will be evaluated using Spearman correlation. To account for potential confounders, multivariable linear regression models will be constructed with myocardial fibrosis or oxidative metabolism as the dependent variable, myocardial blood flow reserve as the primary independent variable with adjustments for age, gender, race/ethnicity, anti-hypertensive medications, systolic blood pressure, heart rate, body mass index, LVEF, LV end diastolic volume, LV mass, and study group. We will check model fit by residual plots. Prior to entry into regression models non-normally distributed variables will be appropriately transformed.

Statistical power for Aim 4: We present different margins of error for the Spearman correlation coefficient based upon different sample sizes and correlation coefficients in **Table 7**.

Based upon a sample size of 60 subjects, modest correlation coefficients of |0.40| to |0.50| would have 0.24 and 0.22 margins of error, respectively.

Sample Size	Correlation coefficient (absolute value)			
	0.2	0.3	0.4	0.5
40	0.32	0.31	0.30	0.28
50	0.28	0.28	0.26	0.24
60	0.26	0.25	0.24	0.22

4. Data Management

Patient clinical data is stored in Vanderbilt's electronic medical record. The hospital database is password protected and accessible only to the appropriate personnel. Research data will be labeled with a patient study code and stored in a separate research database. The code key connecting names to specific information will be available only to members of the research staff and will be kept in a separate, secure location.

The research data will be stored in a HIPPA-compliant manner in a REDCap database accessible to only the PI and key study personnel. Only those personnel that are directly involved in the study will have access to this database.

5. Safety Reporting

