11C-Acetate Positron Emission Tomography for the assessment of oxidative metabolism. We will follow an established protocol for 11C-Acetate PET imaging previously used within our lab.⁶ An intravenous line will be placed in an upper extremity by trained personnel. The subject will then lie supine on the PET/CT scanner and heart rate and blood pressure will be recorded at baseline and every 5 minutes. A limited transmission CT scan of the chest will be performed for

attenuation correction. ^{11}C -Acetate (0.286 mCi/Kg) will then be injected intravenously and PET imaging will begin. ECG gated images will be acquired in list mode for 30 minutes and reformatted into images of 12 frames of 10 seconds each, 8 frames of 30 seconds, 4 frames of 60 seconds, 2 frames of 300 seconds, and 1 frame of 600 seconds. The ^{11}C -Acetate images will be processed following CT attenuation correction. If the images are uninterpretable due to factors such as patient motion, attenuation artifacts, and/or inability to accurately gate images with ECG, then the subject will be withdrawn from the study with attempts to replace the subject to maintain sample size. Regions of interest over the LV blood pool and LV myocardium from the last image of the study will be applied to all preceding frames. Counts in the regions of interest will be determined and expressed as counts/pixel. The blood pool and LV myocardium activities will be plotted against time. The mono-exponential clearance rate, defined as K_{mono} , will be determined by least-squares fitting of the linear portion of the time-activity curve. K_{mono} has previously been demonstrated to correlate with myocardial oxygen consumption.¹⁹⁻²¹ As the rate of cardiac metabolism may be influenced by cardiac demand, LV efficiency will be calculated as the work-metabolic index (WMI) using the equation $\text{WMI} = (\text{LVSVI} \times \text{SBP} \times \text{HR}) / K_{\text{mono}}$, where LVSVI is the LV stroke volume index (stroke volume/body surface area), SBP is systolic blood pressure, and HR is heart rate.²² In addition, oxidative metabolism may be influenced by blood supply, and therefore we will also assess myocardial blood flow through cMRI and PET as described below.

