- B) Myocardial blood flow reserve by Gd enhanced cMRI (MPRI) is correlated with CFR by ¹³N-Ammonia PET.
- C) Subendocardial MPRI is lower than subepicardial MPRI in HFpEF.
- D) Subendocardial MPRI is progressively impaired from healthy to hypertensive to HFpEF.
- E) Myocardial blood flow reserve is positively correlated with LV diastolic function.
- F) Myocardial blood flow reserve is positively correlated with LV systolic function.

Analysis for aim 1. Primary outcome: Myocardial blood flow reserve, as measured by MPRI from contrast enhanced cMRI first pass perfusion imaging and CFR from ¹³N-Ammonia PET perfusion imaging will be compared between the three study groups: healthy, hypertensives, and HFpEF. The distributions of each within each study group will be assessed using histograms, Q norm plots, and the Shapiro Wilk test. If normally distributed then analysis of variance will be used to test for differences in myocardial blood flow reserve between groups. If the p-value from the ANOVA is < 0.05, then pairwise comparisons using unpaired t-tests with unequal variances will be made between groups using a Bonferroni correction. If MPRI or CFR is not normally distributed, then a Kruskal-Wallis test and Wilcoxon rank sum tests will be used in place of ANOVA and t-tests. The null hypothesis is that myocardial blood flow reserve does not differ among HFpEF patients, healthy individuals, and hypertensive individuals. We will also assess correlations (Spearman) between myocardial blood flow reserve, age, gender, blood pressure, heart rate, and body mass index. To account for potential confounders, multivariable linear regression models will be constructed with myocardial blood flow reserve as the dependent variable, study group as the primary independent variable, with adjustments for age, gender, race/ethnicity, anti-hypertensive medications, systolic blood pressure, heart rate, body mass index, LVEF, LV end diastolic volume, and LV mass. Prior to entry into models, variables will be log transformed, as appropriate. We will check model fit by residual plots. Missing data will not be imputed as we will attempt to replace subjects with significant amounts of missing data due to uninterpretable images, as detailed above.

Statistical power for Aim 1: Using a one-way ANOVA at $p = 0.05$, we present between group differences in myocardial blood flow reserve as assessed by CFR under different sample size and power scenarios in **Table 4**. We anticipate

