Aim 3. To compare myocardial fibrosis in individuals with HFpEF versus healthy individuals and those with hypertension.

Primary Hypothesis: Compared with healthy and hypertensive individuals, subjects with HFpEF have increased myocardial fibrosis.

Secondary Hypotheses:

- A) Myocardial fibrosis progressively increases from healthy, to hypertensive, to HFpEF.
- B) Myocardial fibrosis is inversely correlated with LV diastolic function.
- C) Myocardial fibrosis is inversely correlated with LV systolic function.

Analysis for aim 3. Primary outcome: myocardial fibrosis assessed by T1 relaxation times by cMRI will be compared between the three study groups. The analyses for aim 3 will be the same as for aim 2, except that myocardial fibrosis, instead of oxidative metabolism, will be

compared. The distribution of T1 relaxation times, as a measure of myocardial fibrosis, within each study group will be assessed. Based upon distributions, ANOVA or Kruskal-Wallis tests will be used to identify differences between study groups and if significant $p < 0.05$, then pairwise comparisons with T-tests or Wilcoxon rank sum tests will be performed with Bonferroni correction. The null hypothesis is that T1 relaxation times do not differ among HFpEF, healthy, and hypertensive individuals. We will also check for correlations (Spearman) between myocardial fibrosis, age, gender, blood pressure, heart rate, body mass index, and resting myocardial blood flow. To account for potential confounders, multivariable linear regression models will be constructed with myocardial fibrosis as the dependent variable, with adjustments for the same covariates described for oxidative metabolism above.

Statistical power for Aim 3: Using an ANOVA at $p = 0.05$, we present between group differences in T1 relaxation times (msec) under different sample size and power scenarios in **Table 6**. We anticipate having 80% power to detect a between

Healthy	Sample size			Power			SD
	HTN	HFpEF	0.90	0.80	0.70		
20	20	20	70	60	54	60	
15	15	15	80	70	64	60	
25	25	25	60	54	48	60	

ANOVA calculations based upon mean estimated T1 relaxation time in HFpEF of 381 ± 51 msec.⁴¹

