5.1 Serious Adverse Events

Definitions of Serious Adverse Events

A serious adverse event or reaction is any untoward medical occurrence that at any dose:

- Results in death;
- Is life-threatening
(Defined as an event in which the patient was at risk of death at the time of the event; it does not refer to an event which hypothetically might have caused death if it were more severe.);
- Requires inpatient hospitalization or prolongation of existing hospitalization;
- Results in persistent or significant disability/incapacity;
- Results in a congenital anomaly or birth defect;
- Results in the development of drug dependency or drug abuse;
- Is an important medical event-
(Defined as a medical event(s) that may not be immediately life-threatening or result in death or hospitalization but, based upon appropriate medical and scientific judgment, may jeopardize the patient/subject or may require intervention (e.g., medical, surgical) to prevent one of the other serious events or reactions listed above. Examples of such events include, but are not limited to, intensive treatment in an emergency room or at home for allergic bronchospasm and blood dyscrasias or convulsions that do not result in hospitalization. For reporting purposes, Lantheus also considers the occurrences of pregnancy, cancer or overdose (regardless of adverse outcome) as events which must be reported as important medical events.)

SAE Reporting to Regulatory Bodies

Regardless of causality, all SAEs will be documented and reported to regulatory bodies, including the IRB as required by the International Conference on Harmonization (ICH) Guidelines for Good Clinical Practice (GCP). Follow-up information for SAEs and information for non-serious AEs that become serious will also be reported in the same manner.

SAE's will be reported to the Vanderbilt Human Research Protection Program according to institutional policies and procedures.

Study Withdraw/Discontinuation

Patients who wish to be withdrawn from the study will notify the PI who will have any of their data that has not been used or analyzed removed from the REDCap database.

Privacy/Confidentiality Issues

Patient privacy and confidentiality will be protected by the usual practices of the echocardiography laboratory. The confidentiality of patient data will be protected by

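### One uninterpretable acetate scan withdraws the subject from the whole study, although Aims 1 and 3 use no acetate data

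*Combined protocol and SAP*

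**What the plan says.** Section 2.3, in the paragraph on 11C-acetate PET, gives the trigger: "If the images are uninterpretable due to factors such as patient motion, attenuation artifacts, and/or inability to accurately gate images with ECG". The consequence follows: "then the subject will be withdrawn from the study with attempts to replace the subject to maintain sample size". Nothing limits the withdrawal to Aim 2. The protocol-visit text in the same section uses the same withdrawal wording for anaemia, low eGFR and a positive pregnancy test, where it means that the subject leaves altogether. The cMRI and ammonia PET paragraphs contain no image-failure rule.

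Section 3 relies on replacement in its handling of missing data. Under Aim 1: "Missing data will not be imputed as we will attempt to replace subjects with significant amounts of missing data due to uninterpretable images", with a reference back to earlier detail. Aim 2 repeats this, and Aim 3 follows Aim 2.

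The outcomes come from different scans. Aim 1 compares blood flow reserve "as measured by MPRI from contrast enhanced cMRI first pass perfusion imaging" and by CFR from ammonia PET. For Aim 3, "myocardial fibrosis assessed by T1 relaxation times by cMRI will be compared between the three study groups". The Aim 4 analysis set begins "For all subjects completing gadolinium enhanced cMRI myocardial perfusion imaging" and goes on to require the ammonia, acetate and fibrosis scans as well.

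The only rule on removing data is in Section 5, for patients who ask to leave: the investigator "will have any of their data that has not been used or analyzed removed from the REDCap database".

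**The concern.** A technical failure in one modality decides whether a subject counts in every aim. The Specific Aims present acetate PET as an addition for subjects already enrolled in Aim 1, so failure of the added scan removes someone from the base cohort.

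Two things are at stake. The first is precision in Aims 1 and 3 if the withdrawn subjects are not replaced, since replacement is only to be attempted. The second is who remains. Motion, attenuation artefact and poor gating could be commoner in one group than another. Replacing failures with people who scan well would then change the composition of that group in aims that have nothing to do with acetate. Replacement restores the number of subjects but does not undo this.

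**Working it through.** **1. Do Aims 1 and 3 need acetate data?** The Aim 1 outcomes are MPRI (cMRI) and CFR (ammonia PET). Its model adjusts for age, gender, race/ethnicity, anti-hypertensive medication, systolic pressure, heart rate, body mass index, LVEF, LV end-diastolic volume and LV mass. The Aim 3 outcome is T1 (cMRI), with the same covariates plus resting myocardial blood flow, which comes from perfusion imaging. None of these requires acetate.

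**2. What happens to the other scans?** Table 3 lists acetate PET on day 1 ahead of rest/stress cMRI, with fibrosis cMRI and ammonia PET on day 2. The documents do not say when interpretability is judged.
- If it is judged at once, the other scans may never be done.
- If it is judged later, completed scans may go unanalysed.
- If partial data were meant to be kept, the acetate rule conflicts with the Aim 1 text, which reserves replacement for substantial missingness, and with Aim 4, the only aim restricted to subjects completing all four scans.

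No analysis set is defined for Aims 1 to 3, so the question stays open.

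**3. Reproducing the plan's power.** Inputs from Section 3: three groups of 20; ANOVA at 0.05; SD 0.90 (CFR) and 60 msec (T1). Assumption: the middle group lies midway between the extremes. The noncentrality is then

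λ = n·d² / (2·SD²), with 2 and 3n − 3 degrees of freedom.

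- T1, d = 60, n = 20: λ = 20 × 3600 / 7200 = 10.0; power 79.3% against the stated 80%. Reproduced.
- CFR, d = 0.87, n = 20: λ = 20 × 0.7569 / 1.62 = 9.34; power 76.4% against the stated 80%. Not reproduced; 80% needs d = 0.907. This is a separate matter, but 0.907 is the baseline used below.
- The plan's 25% loss, n = 15: CFR 1.05 gives λ = 15 × 1.1025 / 1.62 = 10.2, and T1 70 msec gives λ = 15 × 4900 / 7200 = 10.2; power is 79.4% for both. Reproduced.

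**4. Loss without replacement.** The failure rate is not given. Assume 5% to 15%: 0.05 × 60 = 3 to 0.15 × 60 = 9 subjects, spread evenly, so 19 to 17 per group.

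| n per group | CFR detectable at 80% | Power for CFR 0.87 | T1 detectable at 80% (msec) | Power for T1 60 msec |
|---|---|---|---|---|
| 20 | 0.907 | 76.4% | 60.5 | 79.3% |
| 19 | 0.932 | 74.0% | 62.1 | 77.0% |
| 18 | 0.959 | 71.3% | 63.9 | 74.4% |
| 17 | 0.989 | 68.5% | 65.9 | 71.6% |
| 15 (plan's 25% loss) | 1.058 | 62.2% | 70.5 | 65.4% |

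If three subjects were lost from the HFpEF group alone (20/20/17), power would be 72.5% for CFR 0.87 and 75.6% for T1 60 msec.

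**5. Loss with full replacement.** The sample size and power are unchanged. What remains is the extra recruitment and any selection, which cannot be sized because the documents give no failure rates by group.

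**The case against.** The case for leaving the rule alone has real content. One cohort is enrolled for all aims, and Aim 4, a primary hypothesis, needs acetate, flow and fibrosis in the same person. Keeping a single complete-data cohort of 60 is a defensible aim in a mechanistic study. The plan also tabulates a 25% reduction for dropout and uninterpretable images, and the assumed losses are smaller. Even at 17 per group, the detectable differences stay within the contrasts the plan cites: CFR 3.17 − 2.18 = 0.99 (only just) and T1 459 − 381 = 78 msec. All of that stands and limits the size of the point. It does not justify the rule, because the Aim 4 restriction already secures that aim's complete-data set without removing anyone from Aims 1 and 3.

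Three stronger readings are tempting and are not supported:
- A reader might infer that usable MRI and ammonia data are thrown away. No text says so. The Section 5 removal rule covers only patients who ask to leave, and parts of Section 3 suggest that partial data may be analysed.
- A reader might infer that keeping failures and replacing them gives Aims 1 and 3 63 to 69 subjects (60 plus 3 to 9) with no extra scanning. That holds only if the other scans were already done and usable. Acetate is listed first, and motion or gating trouble may also spoil the same subject's other scans.
- A reader might infer that the rule leaves a fitter HFpEF group and narrows the differences. The direction is unproven. The weight limit and the lie-flat requirement for all groups, and the arrhythmia criteria, restrict the suggested mechanisms without removing them.

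**Conclusion.** The point holds as a flaw in a stated rule. Followed as written, the acetate rule costs Aims 1 and 3 subjects for a failure in a measurement they do not use, and it sits poorly with the missing-data text under Aim 1 and the analysis set for Aim 4. That follows from the text and needs no assumed figure.

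The effect on precision is modest. It rests on an assumed 5-15% failure rate, even loss across groups, no replacement, and a middle group at the midpoint. Under those assumptions the detectable differences rise by about 3-9% for both outcomes (0.932/0.907 to 0.989/0.907; 62.1/60.5 to 65.9/60.5). If replacement succeeds, there is no loss of power. Selection is the more important consequence because replacement cannot correct it, but the documents support neither a size nor a direction. The change is worth making; the issue does not undermine the design.

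**What to change.** Amend the acetate paragraph of Section 2.3 to state that:
- an uninterpretable scan, in any modality, makes that measurement missing;
- the subject completes the remaining imaging and is analysed in every aim whose measurement is usable;
- a replacement may be enrolled for Aims 2 and 4;
- Aim 4 stays restricted to subjects with all four scans.

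In Section 3, define the analysis set for each of Aims 1 to 3 accordingly, align the replacement sentence under Aims 1 and 2 with it, and report scan failures by group and modality so that selection can be judged. The eligibility and safety withdrawals at the protocol visit are not affected.

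The cost is a short protocol change, sample sizes that differ slightly by aim, and the remaining scans still being performed on a subject who is also replaced.

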Healthy	Sample size		Power			SD
	HTN	HFpEF	0.90	0.80	0.70	
20	20	20	1.00	0.87	0.75	0.90
15	15	15	1.20	1.05	0.92	0.90
25	25	25	0.80	0.75	0.60	0.90

ANOVA calculations based upon mean estimated CFR in normals of 3.17 ± 0.88 .³⁹

having 80% power to detect a between group difference (largest to smallest) in mean values of CFR of 0.87, using a conservative estimate for the standard deviation of 0.90 when compared to those reported for normal controls and patients with hypertension, 0.68 and 0.88, respectively.³⁹ The between group difference in CFR is within the range of difference detected between normals (3.17 ± 0.68) and patients with hypertension (2.18 ± 0.88), previously reported.³⁹ Of note even if sample size is reduced by 25%, we still anticipate having good power to detect a between group difference of 1.05. Therefore, using conservative sample sizes that account for potential dropout or uninterpretable images, as well as larger estimates for standard deviation than previously reported, we should have good power to detect plausible differences in myocardial blood flow reserve between HFpEF, healthy, and hypertensive subjects.

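### Aim 1 tests one primary outcome on two measures, MPRI and CFR, with power for CFR only and no rule for which decides or what follows if they differ

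*Combined protocol and SAP*

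**What the plan says.** All of this is in section 3 of the combined protocol and SAP.

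- **Outcome.** Under Analysis for aim 1 the primary outcome is flow reserve, "as measured by MPRI from contrast enhanced cMRI first pass perfusion imaging and CFR" from 13N-Ammonia PET.
- **Separate handling.** The two measures are checked one by one ("The distributions of each within each study group will be assessed"), and the test can switch for one of them: "If MPRI or CFR is not normally distributed, then a Kruskal-Wallis test and Wilcoxon rank sum tests" replace ANOVA and t-tests.
- **Threshold.** "If the p-value from the ANOVA is < 0.05, then pairwise comparisons" follow, and these "will be made between groups using a Bonferroni correction". The correction is for pairs of groups. Nothing divides the 0.05 between MPRI and CFR.
- **Null hypothesis.** It is an overall one: flow reserve is the same in the three groups. The primary hypothesis is directional: HFpEF is lower than both control groups.
- **Power.** Statistical power for Aim 1 presents "between group differences in myocardial blood flow reserve as assessed by CFR" and claims "having 80% power to detect a between group difference (largest to smallest) in mean values of CFR of 0.87", with SD 0.90 and 20 per group. No SD, effect or power is given for MPRI.
- **Agreement of the measures.** This is secondary hypothesis B, examined by Spearman and intraclass correlation.

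No section ranks the two measures, requires both, or says what is concluded if one is significant and the other is not.

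**The concern.** A primary outcome with two measures needs a decision rule, because the error rate and the power both depend on it. The plan states a 5% threshold and 80% power, and both figures belong to a single test on a single measure.

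Without a rule, the choice of headline measure can be made after the results are seen. That matters because the plan does not treat the measures as interchangeable. They come from different scanners on different days with separate regadenoson injections (section 2.3, Table 3), and whether they correlate is itself a study question.

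The gap also carries forward. The adjusted Aim 1 model, the diastolic and systolic function analyses, and the Aim 4 primary analysis all use flow reserve as a variable without saying which measure is meant.

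**Working it through.** **Inputs from the plan.** n = 20 per group, three groups, alpha 0.05 for the overall test, CFR difference (largest to smallest) 0.87, SD 0.90.

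**Assumptions, not in the plan.** The within-group MPRI-CFR correlation r runs from 0 to 0.9. MPRI has the same standardised effect as CFR. Outcomes are normal. For the directional claim, the pairwise tests are two-sided unequal-variance t-tests at 0.05/3.

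**Step 1: the plan's own 80%.** For a one-way ANOVA the noncentrality is λ = n Σ(μᵢ − μ̄)² / SD², with 2 and 57 degrees of freedom.

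- Middle group at the midpoint: λ = 20 × (0.435² + 0 + 0.435²) / 0.81 = 9.34, power 76.4%.
- Middle group equal to one extreme: λ = 20 × (0.29² + 0.29² + 0.58²) / 0.81 = 12.46, power 87.8%.

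The stated 80% lies between the two. At the midpoint, 80% needs a difference of 0.91. This gap is small and is not the point here.

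**Step 2: either measure suffices, no true difference.** With r = 0, the chance that at least one overall test is significant is 1 − 0.95² = 9.75%. For r above 0 it was simulated (40,000 studies per setting): about 9.0% at r = 0.5, 8.4% at 0.7 and 7.3% at 0.9.

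**Step 3: both measures required, difference 0.87.** With r = 0 and the midpoint pattern, joint power is 0.764² = 58.4% (simulated 58.9%). Simulated values:

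| r | Both significant, midpoint | Both significant, extreme | Tests disagree, midpoint | Tests disagree, extreme |
|---|---|---|---|---|
| 0 | 59% | 77% | 36% | 22% |
| 0.3 | 62% | 78% | 30% | 19% |
| 0.5 | 64% | 80% | 26% | 16% |
| 0.7 | 67% | 82% | 20% | 13% |
| 0.9 | 71% | 84% | 11% | 8% |

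Requiring both costs power under either pattern: from 76% to 59%–71% at the midpoint, and from 88% to 77%–84% at the extreme.

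**Step 4: sensitivity of disagreement.** If each measure truly has 80% power and r = 0, disagreement is 2 × 0.8 × 0.2 = 32%; at r = 0.9 it is 11%. If MPRI had only 50% power against 80% for CFR, with r = 0, it is 0.8 × 0.5 + 0.2 × 0.5 = 50%.

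**Step 5: the full directional claim.** This requires a significant overall test and then HFpEF below both controls after Bonferroni.

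- False claims on either measure: about 0.2% when no group differs, and at most about 1.7% when only the healthy group differs.
- Disagreement when the controls are equal and HFpEF is 0.87 lower: 49%, 35%, 27% and 15% at r = 0, 0.5, 0.7 and 0.9, with about 56% power per measure.
- Disagreement when hypertensives are midway: 27% to 9%, with about 16% power per measure.

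**The case against.** The strongest reply is that the primary hypothesis is directional and involves both controls. A significant ANOVA only opens the pairwise tests, and the complete rule is falsely satisfied in about 0.2% of studies with no true difference, even if either measure counts. That is right. A reader might infer that the primary HFpEF claim exceeds 5% error; the calculations do not support this. What remains is the overall null, which the plan itself states as the Aim 1 null hypothesis.

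Second, a reader might infer that the plan lets either measure carry the claim. The text says no such thing. It joins the measures with the word *and*, so a both-required reading is equally open. That reading inflates no error rate but costs power.

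Third, a reader might infer that the measures will often disagree. The documents give no MPRI mean, SD, effect or correlation with CFR, so the disagreement rates are scenarios only. Under equal effects the overall tests agree in most studies.

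Finally, this is a 60-subject mechanistic study in which comparing PET with cMRI is a declared purpose. Both results are planned for analysis, which limits silent selection. It still supplies no rule for the Aim 1 conclusion.

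**Conclusion.** The point holds as a missing decision rule with a measurable consequence. The text establishes two measures under one primary outcome, separate testing at 0.05, power for CFR only, and silence on how they combine.

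- **If either suffices,** the 5% level fails for the overall null, at about 7% to 10% for r from 0.9 to 0.
- **If both are required,** the power statement does not describe the primary conclusion. It is about 59% to 71% at 0.87 with hypertensives midway. If the middle group sits at an extreme, it is 77% to 84%, against 88% for CFR alone.
- **Disagreement** between the overall tests could occur in roughly 10% to 35% of studies (somewhat less under the extreme pattern), with nothing written for that case.

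The power and disagreement figures assume an equal standardised effect on MPRI, and all the ranges depend on an assumed correlation. The inflation does not extend to the claim that HFpEF is below both controls. The change should be made before analysis because it removes an after-the-fact choice at almost no cost.

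**What to change.** In section 3, Analysis for aim 1, name CFR from 13N-Ammonia PET as the single primary outcome, since it is the measure on which Table 4 rests. Make MPRI a supportive secondary outcome that cannot carry the Aim 1 conclusion alone. State that flow reserve means CFR in the Aim 4 primary analysis. Secondary hypotheses B to D, which concern the MPRI-CFR correlation and layer-specific MPRI, stay as they are. The threshold remains 0.05, Table 4 remains the relevant power table, and no extra subjects or scans are needed.

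If the sponsor prefers to keep both as primary, either of these also works, provided MPRI assumptions are given and power is restated:

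- **Both required.** No alpha split is needed; power is as in the table above.
- **Alpha split 0.025 + 0.025.** Family-wise error for the overall null is at most 5%. CFR power at 0.87 falls from 76.4% to 66.4% (midpoint) or from 87.8% to 80.7% (extreme). The difference detectable with 80% power rises from 0.91 to 1.00 (midpoint).

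The cost of the preferred change is a few sentences and one small loss: a positive MPRI with a negative CFR could no longer be reported as a positive Aim 1.
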